1.2. Oseltamivir

Oseltamivir (Tamiflu)

Oseltamivir is an influenza neuraminidase inhibitor indicated for the treatment of acute, uncomplicated influenza infection in patients 2 weeks of age and older who have been symptomatic for no more than 2 days and for prophylaxis of influenza in patients 1 year and older.

Clinical studies have shown that treatment with oseltamivir has clinical and virological benefit in patients with uncomplicated influenza when administered within 48 hours of onset of symptoms. Randomized studies in patients with severe influenza are lacking, but observational studies in patients admitted to hospital suggest that oseltamivir treatment, especially if it is given early, is associated with reduced mortality and shorter length of stay.³

Higher oseltamivir doses were tested in patients with uncomplicated influenza, but clinical or virological outcomes were found not significantly different compared to the standard dose. Despite a lack of evidence, several health authorities, including the United States Centers of Disease Control and Prevention (CDC) are recommending the use of double dose oseltamivir for severely ill or immunocompromised with influenza.¹³

There have been no studies specifically designed to evaluate the effectiveness of extending the duration of oseltamivir treatment beyond 5 days, however, it is reported in literature that over 32% of hospitalized patients carry replicating virus beyond 7 days of illness onset.⁷ Using mathematical simulations to model an early or extended-duration oseltamivir therapy beyond 5 days has shown an increased virological and symptom efficacy and a potential for reduced emergence of resistance. The available data from uncomplicated influenza studies are inconclusive whether reducing viral shedding leads to faster clinical improvement, but there are data supporting that lower viral load results in faster symptom resolution.⁷ Thus, there may be a possible benefit in using oseltamivir beyond 5 days in patients hospitalized with influenza.

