4.2. Exclusion Criteria

Any potential subject who meets any of the following criteria will be excluded from participating in the study.

1. Subject received more than 3 doses of the influenza antiviral medication oseltamivir, zanamivir, or peramivir since the start of the influenza symptoms, or ribavirin within 6 months prior to screening.
2. Subject is unwilling to undergo regular nasal MT swabs or has any physical abnormality which limits the ability to collect regular nasal specimens.
3. Subject is known (considering lab results of the past 6 months) to be severely immunocompromised as defined by a CD4⁺ count <350 cells/mm³ or an absolute neutrophil count <750/mm³.
4. Subject is undergoing peritoneal dialysis, hemodialysis, or hemofiltration.
5. Subject has an eGFR \leq 30 mL/min/1.73m² according to the MDRD equation, assessed at

screening or based on the most recent clinically relevant creatinine value if available.

6. Subject has known moderate (Child-Pugh class B) or severe hepatic impairment (Child-Pugh class C).
7. Subject has presence of any pre-existing illness, clinically significant laboratory abnormalities, ECG findings, or physical examination findings that, in the opinion of the investigator, would place the subject at an unreasonably increased risk through participation in this study. The investigator should consider the laboratory parameter criteria for study drug discontinuation (see Section 9.3.6) when screening a subject for enrollment.
8. Subject with known acute hepatitis A, B, or, C virus infection at screening, or known chronic hepatitis C infection undergoing antiviral therapy.
9. Subject has known allergies, hypersensitivity, or intolerance to JNJ-63623872 or its excipients (refer to the Investigator's Brochure⁶).
10. Subject has contraindications to the use of oseltamivir per local prescribing information.^{14,15}
11. Subject has received an investigational drug (including investigational vaccines) or used an invasive investigational medical device within 30 days, or has received an investigational biological product within 3 months or 5 half-lives (whichever is longer) before the planned first dose of study drug or is currently enrolled in an investigational study.
12. Subject has a history of clinically significant heart arrhythmias, eg, unstable angina or myocardial infarction; uncontrolled, unstable atrial arrhythmia, or sustained ventricular arrhythmia, or a history of risk factors for Torsade de Pointes syndrome.

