3.2. Analysis sets

Population of the analyses covered by this SAP will be:

- *Randomized Analysis Set (RAND)*: All randomized subjects with a randomization date at or before the date of first intake of medication, or with a randomization date and no medication intake.
- *Randomized and/or Treated Analysis Set (RT)*: All randomized subjects and/or all subjects who received at least 1 dose of study drug.
- *Safety Set or All Subjects Treated (AST)*: All subjects who received at least 1 dose of study drug, analyzed as treated.
- *Full Analysis Set (FAS)*: All randomly assigned subjects who receive at least 1 dose of study drug and who have a confirmed infection with influenza A. Confirmation of Influenza A will be obtained from virology data. If there are no virology data available at cut-off of the interim analysis, then a subject will be considered infected with Influenza A and included in the FA set. If there are no virology data available at final analysis, then a subject will be excluded from the FA set. Analyses on the Full Analysis Set will be analyzed as treated.

A subject is considered to have a confirmed infection with influenza A if he/she has:

- at least one positive PCR result from central lab testing¹ (lbtstcd = 'INFAVLD') at baseline or pre-baseline;
else
- at least two positive PCR results from central lab testing¹ (lbtstcd = 'INFAVLD') post-baseline;
else
- at least one positive PCR result from central lab testing¹ (lbtstcd = 'INFAVLD') post-baseline and one positive PCR result from local lab testing (lbtstcd = 'INFVSCR') post-baseline, provided that both are from a separate visit day;
else
- at least one positive PCR result from local lab testing (lbtstcd = 'INFVSCR') at baseline or pre-baseline, provided that no central lab testing is available at baseline or pre-baseline.
else
- at least two positive PCR results from local lab testing (lbtstcd = 'INFVSCR') post-baseline, provided that no central, or local lab testing is available at baseline or pre-baseline, and no central lab testing is available post-baseline.

¹Viral load results from central lab testing (lbtstcd = 'INFAVLD') recorded as 'TARGET NOT DETECTED' will be considered as negative, all other results ('<2.18' and numeric results) as positive.

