Admitted to ICU or mechanically ventilated/ECMO
Non-ICU + supplemental oxygen
Non-ICU + no supplemental oxygen
Not hospitalized, but unable to continue activity
Not hospitalized and continues activities

ECMO = extracorporeal membrane oxygenation; ICU = Intensive Care Unit

4.2.2. *Viral Kinetics*

Influenza viral load and viral titer will be determined and quantified in Nasal MT swab samples taken daily until discharge or until Day 14, whichever comes first. When subjects are discharged from the hospital and still positive for influenza A virus, they are encouraged to perform self-swabbing at home if practically feasible. All swabs will be analyzed using quantitative real time polymerase chain reaction (qRT-PCR) and/or viral culture (TCID₅₀) and/or PCR-based rapid molecular testing (if applicable).

All analyses described below, will be done on the qRT-PCR and viral culture results from central lab testing. As a sensitivity analysis, time to viral negativity will also be evaluated on a combination of the qRT-PCR results from central testing with the local rapid influenza test results (at home or on site) of days on which the results from central lab testing were missing.

The viral culture (TCID₅₀) measurements are analyzed using two methods (depending on influenza subtype); i.e. NP ELISA and Hemagglutination Inhibition Assay. For analysis purposes the results from the NP ELISA method will be used when available, otherwise the results from the Hemagglutination Inhibition Assay will be used. This will be determined per time point. As a consequence the results of a subject can be a combination of both methods (for example at baseline the NP ELISA result is used and at day 4 the Hemagglutination Inhibition Assay result is used).

Viral load results recorded as 'TARGET NOT DETECTED' will be considered as negative, all other results ('<2.18' and numeric results) as positive. Viral titer results recorded as '<0.75' will be considered as negative, all other results as positive.

For analysis purposes the log₁₀ qRT-PCR viral load will be imputed with 2.12 when the result is '<2.18' (i.e. below limit of quantification) and with 0 if result is 'TARGET NOT DETECTED' (i.e. below limit of detection: <2.05). The log₁₀ TCID₅₀ viral titer will be imputed with 0.375 when the result is '<0.750'.

- **Viral load and viral titer actual values and change from baseline**

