Descriptive statistics and mean (SE) plots will be shown for the log₁₀ values of viral load and viral titer (qRT-PCR and viral culture) and the changes from baseline calculated in log₁₀ (vp/mL or TCID₅₀/mL).

- **Incidence of influenza A viral negativity by assessment**

The proportion of subjects with a negative viral load and a negative viral titer will be tabulated at each time point. In addition, per parameter and time point a logistic model with baseline viral load/viral titer and age category (≥ 18 - <65 years, ≥ 65 - ≤ 85 years) as covariates will be used to obtain the odds ratios (95% CI) for the comparison of the incidence of influenza A viral negativity of treatment versus placebo.

Stacked barcharts of the percentage of subjects per response category will be made by day and treatment for viral load and viral titer. The following response categories will be used:

- For viral load (log₁₀ vp/mL) measurements:
 - Target not detected (<2.05 log₁₀ vp/mL)

- Target detected ($<2.18 \log_{10} \text{ vp/mL}$)
- Quantifiable ($\geq 2.18 \log_{10} \text{ vp/mL}$)
- For viral titer ($\log_{10} \text{ TCID}_{50}/\text{mL}$) measurements:
 - Negative ($<0.75 \log_{10} \text{ TCID}_{50}/\text{mL}$)
 - Positive ($\geq 0.75 \log_{10} \text{ TCID}_{50}/\text{mL}$)

- **Time to influenza A viral negativity**

The time to influenza A viral negativity will be determined based on nasal MT swabs: a subject will be considered influenza A viral negative at the time point that the first confirmed negative nasal MT swab was recorded (in days) i.e. defined as time in days from start of treatment to first of assessments = 'negative' and the next assessed measurement is not = 'positive' (ignoring missings, i.e. if first 'negative' is last available assessment or if next assessed result after first 'negative' is also 'negative'). If this doesn't occur, a subject will be censored at the time of the last observed nonnegative swab + 1 day. Note that at baseline every subject is considered positive.

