This will be done separately for viral load and viral titer assessments from central lab testing. As a sensitivity analysis, time to negativity will also be evaluated on a combination of qRT-PCR results from central lab testing and rapid influenza test results (from self or on site swabs). The available central lab qRT-PCR results (qualitative) will be complemented with the results of the rapid influenza tests that are available on days where central lab testing results are not available.

The time to influenza A viral negativity will be presented using Kaplan-Meier curves and Kaplan-Meier estimates by treatment group, overall and by age group. For a comparison between treatment arms, the time to influenza A viral negativity will be analyzed using an accelerated failure time model. The accelerated failure time model will use a Weibull, log-logistic, lognormal or gamma distribution based on goodness of fit criteria (AIC). As covariates the baseline viral load and the age category ($\geq 18 - <65$ years, $\geq 65 - \leq 85$ years) will be included. If the data don't provide an acceptable model fit, alternatively a Cox proportional hazards model can be used (in case the hazards are proportional). In case a Cox proportional hazards model is used a Log-log plot of survival will be added to check the proportional hazard assumption. Additionally, the time to event data will be analyzed using the logrank test and Gehan-Wilcoxon method.

- **Viral AUC calculated from baseline to Day 8**

The viral AUC, calculated separately for viral load and viral titer, from baseline to Day 8 will be estimated for each treatment arm using a mixed model for repeated measurements, i.e., the AUC will not be calculated for each subject and then analyzed, but the AUC will be calculated for each treatment arm using \log_{10} transformed viral load data over time of each subject. This approach ensures an optimal approach towards missing data.

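### Time to culture negativity counts subjects who were culture-negative before dosing as clearing virus after it, which is expected to dilute a true treatment effect

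*SAP*

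**What the plan says.** SAP 4.2.2 defines time to influenza A viral negativity as days from start of treatment to the first negative swab that is not followed by a positive result. It adds "Note that at baseline every subject is considered positive", and continues: "This will be done separately for viral load and viral titer assessments from central lab testing". For culture, the same section says "Viral titer results recorded as '<0.75' will be considered as negative, all other results as positive"; for computation such results are set to 0.375.

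The Full Analysis Set (SAP 3.2) has no culture criterion. Its first route is "at least one positive PCR result from central lab testing" at or before baseline. Another route accepts a local PCR result, "provided that no central lab testing is available at baseline or pre-baseline". Culture may also be lacking: "All swabs will be analyzed using quantitative real time polymerase chain reaction (qRT-PCR) and/or viral culture".

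The accelerated failure time model adjusts for baseline viral load and age category. The neighbouring logistic model names viral load or viral titer to match the outcome; the time-to-event text does not.

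For vital signs (SAP 4.2.1), subjects who already meet the criteria at entry are censored there. Protocol 11.6 notes that this amounts to excluding them. Protocol 11.6 has no deemed-positive rule for virus.

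Peak viral load or titer (SAP 4.2.2) is the maximum including the baseline value. It is modelled on treatment, age category and their interaction.

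**The concern.** For PCR, deeming everyone positive at baseline fits an analysis set defined by PCR. For culture, it overrides a measured result. A subject with no culturable virus before the first dose cannot clear culturable virus because of that dose, yet is scored as an early success in both arms.

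Such subjects are plausible. Protocol 4.1 and 4.2 set no limit on time since symptom onset. The antiviral exclusion applies only if "Subject received more than 3 doses of the influenza antiviral medication oseltamivir, zanamivir, or peramivir since the start of the influenza symptoms", so up to 3 doses are allowed. Protocol 1.2 cites that "over 32% of hospitalized patients carry replicating virus beyond 7 days of illness onset", which leaves up to 68% who do not.

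Culture negativity is part of secondary objective 2, and SAP 4.2.8 correlates the same times with five clinical measures. A real antiviral effect could look smaller than it is.

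The peak has a related problem. If virus is already falling at entry, the maximum is often fixed before any drug is given.

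**Working it through.** The plan gives no effect size, event count or precision for these endpoints, so there is no figure to reproduce. From the documents come the 60:30 split (up to 90 subjects, 2:1), the confirmation and censoring rules, the covariates, the model choices, the post-discharge swab days and the imputed values. Everything else is assumed.

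**1. Time ratio, by formula.** Let p be the baseline culture-negative share, with the same earliest event time in both arms. The difference in mean log time is then (1 - p) x log(TR) + p x 0, so the apparent ratio is TR^(1-p). A true 0.70 becomes 0.74 on the swab days, and ln 0.74 = -0.301. At 20%: exp(0.8 x -0.301) = 0.79.

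**2. Time ratio, by simulation.** Control median 3 days, log-SD 0.6, 900 trials per row, distribution chosen by AIC from Weibull, log-logistic and lognormal (gamma not fitted).

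| p | 0.74^(1-p) | Planned analysis | Baseline culture-positives only | Log effect lost | Loss / trial-level SD |
|---|---|---|---|---|---|
| 2% | 0.74 | 0.74 | 0.74 | 2% | 0.04 |
| 5% | 0.75 | 0.75 | 0.74 | 4% | 0.08 |
| 10% | 0.76 | 0.76 | 0.74 | 9% | 0.19 |
| 20% | 0.79 | 0.78 | 0.74 | 20% | 0.41 |
| 30% | 0.81 | 0.81 | 0.74 | 31% | 0.58 |

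- The planned ratio is the higher of the two in 62% of trials at 10%, 69% at 20% and 74% at 30%. A single trial can go either way.
- If 20% of the negatives later grow virus, the losses are 1, 4, 9, 19 and 30%.
- Using titer as covariate but keeping the negatives gives 0.79 at 20% and 0.82 at 30%, so the covariate alone does not repair it.
- With no true effect, the planned rule gives 1.01 at 20% negative.
- With 10% of baseline cultures missing at random, excluding those subjects gives 0.74 and deeming them positive gives 0.74-0.75.

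**3. Dependence on the fitted distribution.** In separate large-sample fits with a true ratio of 0.70, adjusted for baseline viral load, the lognormal ratio moved from 0.72 at p = 0 to 0.78 at 20% and 0.80 at 30%. Weibull moved from 0.73 to 0.75 and 0.75. Lognormal fitted best there, but the data had been generated as lognormal.

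**4. Titer AUC and slope.** A subject negative throughout is a flat line at 0.375 in both arms. The arm difference at each visit is (1 - p) x d(t) + p x (0.375 - 0.375) = (1 - p) x d(t). AUC is linear in the visit means, so it loses the fraction p. A numerical check at p = 20%, with assumed declines of 0.4 and 0.7 log10/day, gave an AUC difference of -3.80 instead of -4.65 (0.85/4.65 = 18% lost) and a slope difference of -0.071 instead of -0.091 (0.020/0.091 = 22% lost).

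**5. Rough link to Protocol 1.2.** If 3, 15 or 30% of subjects enrolled beyond day 7 of illness (assumed) and 68% of those were culture-negative, p would be 2, 10 or 20% (0.03, 0.15, 0.30 x 0.68). Requiring a positive PCR would lower this.

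**6. Peak.** Assumed slopes -0.5 (control) and -0.8 (active) log10/day, assay SD 0.3-0.7.

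| Still rising at entry | Effect, peak including baseline (log10) | Effect, post-baseline peak (log10) | Share kept |
|---|---|---|---|
| 0% | -0.013 to -0.101 | -0.315 to -0.404 | 4-25% |
| 50% | -0.161 to -0.215 | -0.318 to -0.408 | 51-53% |

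With none rising, baseline is the peak in 61-97% of subjects. In a second set of scenarios, adding a baseline covariate to the planned peak changed its mean effect by at most 0.02 log10. The loss comes from the definition, not from the missing covariate.

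**The case against.** **The share is unknown.** No document gives it, screening and dosing are meant to be prompt, and prior antivirals are capped. This stands: at 2% nothing is lost, and at 10% the shift is 0.02 in the ratio.

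**The size depends on the model.** This also stands. If AIC selects Weibull, most of the shift disappears.

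**The plan already shows part of it.** It summarises baseline titer and tabulates negative titer by time point, and Kaplan-Meier curves would show early events. That helps a reader see the problem but does not correct the estimate, and the only planned sensitivity analysis adds rapid tests to PCR.

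**One pre-dose negative is unconfirmed.** Some of these subjects will later grow virus. This is a real cost of restricting, and the reason to keep the full-set analysis.

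A reader might infer that titer AUC and rate of decline escape, because they do not use the deemed-positive rule. They do not: the imputed 0.375 dilutes them to a similar degree. The root is culture analysed in a PCR-defined set, and the baseline rule is its plainest expression.

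A reader might also infer that peak cannot respond to treatment at all. The documents do not support that. Protocol 1.3 reports a reduced peak in the challenge study, where dosing began 24 hours after inoculation, and about half the effect survives here if half the subjects are still rising. A whole-course maximum is also a legitimate estimand. The absent baseline covariate costs precision and lets chance imbalance through, but does not bias the randomised comparison.

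**Conclusion.** The point holds for viral culture; the PCR rule is not at fault. The text does count pre-dose culture-negatives who stay negative as post-dose clearance, and the expected direction is towards a ratio of 1 whenever there is a true effect. Under lognormal times the fraction of the log effect lost is about equal to the baseline-negative share: material from roughly 10-20%, negligible near 2%. It is much smaller under Weibull. Titer AUC and slope lose a similar fraction. All of this rests on an assumed share, an assumed effect and assumed time distributions.

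The peak definition is a secondary point: largely insensitive when the peak precedes dosing, less so otherwise.

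These are exploratory estimates without formal testing, so no error rate or sample size is affected. The change is still worth making, because a secondary objective is involved and the SAP already handles the same situation differently for vital signs.

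**What to change.** **Time to negativity, viral titer only**
- Run the main analysis in subjects with baseline titer of at least 0.75, or censor the others at entry as for vital signs. Name baseline titer as the covariate.
- Exclude subjects with no baseline culture result from the main analysis.
- Keep the full-set analysis, including both groups, as a sensitivity analysis.
- Show baseline culture-negative counts by arm.
- Leave the PCR rule unchanged.

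**Titer AUC and rate of decline:** repeat both in the baseline-culture-positive subset as a sensitivity analysis.

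**Peak:** add a comparison of the highest post-baseline value, adjusted for the matching baseline load or titer. Keep the whole-course peak as a descriptive summary.

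**Cost:** SAP wording and code, no new data. The restriction uses a pre-dose measurement, so it keeps the randomised comparison. The main culture analysis becomes smaller: 90 x 0.80 = 72 subjects at 20% negative, and about 65 (72 x 0.90) if a further 10% lack a baseline culture. Subjects who turn culture-positive later appear only in the sensitivity analysis.

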4.2.3. Influenza Symptom Score (FLU-iiQTM Module 1)

The influenza symptom score (Flu-iiQTM Modules 1) will be assessed 2 times a day, from study entry (Baseline, Day 1) through Day 14, and once daily from Days 15 through Day 28 (Safety Follow-up Visit).

- **Composite symptom score**

The subject's composite symptom score per datetime is defined as the mean of the corresponding non-missing 7 primary influenza symptoms of the Flu-iiQTM (cough, sore throat, headache, nasal congestion, feeling feverish, body aches or pains, and fatigue (tiredness)) on a 0-3 scale calculated for each datetime the questionnaire was filled. For each time point a change from baseline will be calculated.

An alternative composite symptom score will be calculated using all 10 influenza symptoms included in Module 1 of the Flu-iiQTM instrument.

If more than 50% of the items to construct a Composite symptom score are missing, the value for that composite score is coded as missing (i.e. 4 or more items missing for the primary symptom composite score and 6 or more items missing for the composite score based on all 10 items).

The actual composite symptom scores and changes from baseline will be shown descriptively and by mean (SE) plots per analysis timepoint.

- **Daily average symptom score**

For the Flu-iiQTM a daily average symptom score will be derived averaging the composite symptom scores (based on 7 primary and all 10 items respectively) per day over all post-baseline analysis timepoints. Also a total average symptom score over the daily averages of the composite symptom score will be calculated. The baseline value of the daily average symptom score will be the baseline score of the respective individual influenza symptom score or the composite symptom score..

The daily averages of the composite symptom scores will be shown descriptively and by mean (SE) plots. The total average composite symptom score will be shown descriptively.

- **Time to Resolution of Influenza**

Resolution of influenza symptoms is defined as the first of a successive series of 2 recordings in which all symptom scores for each of the 2 assessments are 0 or 1 for all 7 primary influenza symptoms of the Flu-iiQTM (cough, sore throat, headache, nasal congestion, feeling feverish, body aches or pains, and fatigue (tiredness)). If the first record of a successive series of 2 recordings of resolved influenza is before day 14 in the evening then the 2 successive recordings should have been done over 3 scheduled successive analysis timepoints, 1 missing timepoint is allowed. If the first record of a successive series of 2 recordings of resolved influenza is at or after the evening record of Day 14 then the 2 successive recordings should have been done within 2 scheduled successive analysis timepoints (no missing allowed).

In cases where there are no sufficient recordings of resolved influenza as defined above, the endpoint will be censored. Censoring will be at the first

time of resolved influenza symptoms, if and only if after this observation there is no recording of non-resolved influenza symptoms (ignoring missing recordings). If there are no recordings of resolved symptoms satisfying this criterion, the time of censoring is the first possible time point a diary entry could have been made after the last observation of the presence of influenza, which is 20:00 on the same day if the last observation was a morning diary entry (from 3:01 until 15:00), 8:00 the next day if the last entry was an evening diary (from 15:01 until 03:00) (Day 1 until Day 14, morning). If the last observation of the presence of influenza is on Day 14 in the evening or after day 14 then the time of censoring is the time of the last diary entry + 24 hours. One exception is censoring at the Day 28 Visit (last study day for the subject). If the subject is not recovered on this day, the time of the last diary entry will be taken as the time of censoring.

Subjects who discontinue the study before resolving influenza symptoms and have an adverse events being reported as influenza complication ongoing on the day of discontinuation of the study will be censored at day 28, 20:00.

For this endpoint the difference of active dosing regimen versus placebo will be estimated using the accelerated failure time model. The model will use the parametric shape, selected based on the goodness of fit criterion (AIC), and may take a Weibull, log-logistic, lognormal, or gamma distribution. As baseline covariates the baseline composite score and age category (≥ 18 - < 65 years, ≥ 65 - ≤ 85 years) will be included. From this model the ratio of adjusted geometric means and the 95% confidence interval will be derived comparing the active treatment versus placebo.

The Kaplan-Meier estimates will be tabulated and a figure with the Kaplan-Meier curves of the time to resolution of influenza symptoms will be added by treatment group, overall and by age group.

One stratified Cox proportional hazard model will be used to derive the Hazard Ratio for the active treatment in comparison to placebo. A Log (-Log) plot of survival will be added to check the proportional hazard assumption. Additionally, the time to event data will be analyzed using the logrank test and the Gehan-Wilcoxon method.

All analyses of Time to Resolution of Influenza will also be repeated using all 10 influenza symptoms included in Module 1 of the Flu-iiQTM instrument.

Kaplan-Meier curves will also be provided for each individual influenza symptom separately.

▪ **Time to Definitive Resolution of Influenza**

Time to definitive resolution is defined as the first of a successive series of 2 recordings in which all symptom scores for each of the 2 assessments are 0 or 1 for all 7 primary influenza symptoms of the Flu-iiQTM (cough, sore throat, headache, nasal congestion, feeling feverish, body aches or pains, and fatigue (tiredness)) AND after which all following assessments also indicate resolution (all symptom scores 0 or 1 for all 7 primary influenza symptoms) or are missing.

Definitions for a successive series of 2 recordings over time are the same as for the Time to Resolution of Influenza. Also censoring will be done similarly as for the Time to Resolution of Influenza.

The Time to Definitive Resolution of Influenza will be analyzed similarly as the Time to Resolution of Influenza.

▪ **Composite symptom score AUC:**

The composite symptom score AUC will be calculated using the daily average symptom scores, from baseline to Day 8 and will be estimated for each treatment arm using a mixed model for repeated measurements, ie, the AUC will not be calculated for each subject and then analyzed, but the AUC will be calculated for each treatment arm using the daily average symptom scores over time of each subject. This approach ensures an optimal approach towards missing data.

Baseline and post-baseline daily average symptom scores over time will be analyzed using a restricted maximum likelihood based repeated measures approach and using a constrained longitudinal data analysis. The analysis model will include the fixed, categorical effects visit, treatment-by-visit interaction, age category-by-visit interaction and treatment-by-visit-by age category interaction.

The following list of covariance structures will be applied in the model fit, in the specified order, and the first correlation structure to yield convergence will be applied in the analysis:

- Unstructured [UN]
- Ante-dependence [ANTE(1)]
- Heterogenous Toeplitz [TOEPH]
- Heterogeneous CS [CSH]
- Heterogeneous AR(1) [ARH(1)]
- Toeplitz [TOEP]

The Kenward-Roger approximation will be used to estimate denominator degrees of freedom.

The composite symptom score AUCs until Day 8 will be based on the Full Analysis set. The model estimates from the model above will be used to estimate the composite symptom score AUCs for each treatment and to derive the difference in the composite symptom score AUCs for active versus placebo overall and by age category.

A mean $\pm 95\%$ CI plot will also be provided for the estimated average symptom scores over time.

4.2.4. *Impact of Influenza (Flu-iiQTM Modules 2, 3, 4)*

The impact of influenza (Flu-iiQTM Modules 2, 3, 4) will be assessed 2 times a day, from study entry (Baseline, Day 1) through Day 14, and once daily from Days 15 through Day 28 (Safety Follow-up Visit).

- **Composite impact score**

Per datetime and per module (modules 2, 3 and 4) of the FLU-iiQ™ questionnaire a composite impact score will be calculated as the mean of the non-missing items in each module respectively on a 0-3 scale. Additionally a “total composite impact score” will be calculated as the mean of all non-missing items over all 3 impact score modules together (15 questions). For each time point and composite impact score (module 2, 3,4 and total) a change from baseline will be calculated. If more than 50% of the items to construct a Composite Impact Score are missing, then the value for that composite score for that individual and time point is coded as missing (i.e. 4 or more items missing for module 2, 3 or more items missing for module 3, 3 or more items missing for module 4 and 8 or more items missing for the total composite impact score).

The composite impact scores will be shown descriptively and by mean (SE) plots per analysis time point.

- **Daily average impact score**

For the impact modules of the FLU-iiQ™ questionnaire a daily average of the composite impact scores (for modules 2,3,4 and total) and a total average score over the daily averages of the composite impact scores (for modules 2,3,4 and total) will be calculated similar to the daily average symptom scores above.

The daily averages of the composite impact scores will be shown descriptively and by mean (SE) plots. The total average composite impact scores will be shown only descriptively.

- **Time to resumption of normal activities (usual activities, emotional impact and impact on others)**

Per module of the FLU-iiQ™ questionnaire on the impact of influenza a time to resumption of normal activities is defined as the time in hours from the first dose of investigational product till the first one of a successive series of 2 recordings where all scores in the FLU-iiQ Module are reported as “no difficulty” (Module 2: usual activities), “not at all” (Module 3: emotional impact) or “not at all concerned” (Module 4: impact on others). If the first record of a successive series of 2 recordings of resumption of normal activities is before day 14 in the evening then the 2 successive recording should have been done over 3 scheduled successive analysis timepoints, 1 missing timepoint is allowed. If the first record of a successive series of 2 recordings of resumption of normal activities is at or after the evening record of Day 14 then the 2 successive recording should have been done within 2 scheduled successive analysis time points.

Censoring will be done similar to the time to resolution of influenza, taking into account the possible time points a diary entry could have been made after the last observation of difficulties in usual activities, which is 20:00 on the same day if the last observation was a morning diary entry and 8:00 the next day if the last entry was an evening diary entry (Day 1 until Day 14, morning). If the last observation of difficulties in usual activities is on Day 14 in the evening or after Day 14 then the time of censoring is the time of the last diary entry + 24 hours. One exception: if no resumption of usual activities is

observed at Day 28, the time of the last diary entry will be taken as the time of censoring

Data will be presented using Kaplan-Meier curves and Kaplan-Meier estimates by treatment group, overall and by age group. For a comparison between treatment arms, the time to parameters will be analyzed using an accelerated failure time model. The model will use the parametric shape, selected based on the goodness of fit criterion (AIC), and may take a Weibull, log-logistic, lognormal, or gamma distribution. As baseline covariates the respective baseline composite impact scores and age category (≥ 18 - < 65 years, ≥ 65 - ≤ 85 years) will be included. If the data don't provide an acceptable model fit, alternatively a Cox proportional hazards model can be used (in case the hazards are proportional). In case a Cox proportional hazards model is used a Log-log plot of survival will be added to check the proportional hazard assumption. Additionally, the time to event data will be analyzed using the logrank test and Gehan-Wilcoxon method.

4.2.5. *FLU-iiQTM Additional Daily Diary Items*

For the 5 additional daily diary items of FLU-iiQTM frequency distributions of the number (%) of subjects per additional FLU-iiQTM item and per response category will be shown at baseline and all post-baseline assessments, per treatment group.

4.2.6. *Influenza Patient Reported Outcome Diary (FLU-PRO)*

- **FLU-PRO total score and FLU-PRO domain scores**

The FLU-PRO total score is computed as a mean score across 32 items contained by the instrument. Total scores can range from 0 (symptom free) to 4 (very severe symptoms).

Six FLU-PRO domain scores are computed, representing symptom severity in each of the following body areas: Nose, Throat, Eyes, Chest/Respiratory, Gastrointestinal and Body/Systemic. Each domain score is calculated as the mean of all items comprising the domain, see also Table 8. Each FLU-PRO domain score ranges from 0 to 4.

These scores will be calculated at each time point a questionnaire was filled. A change from baseline will also be calculated.

The FLU-PRO scores and changes from baseline will be presented descriptively over time.

Table 8: FLU-PRO domain scores

Domain	Items	Scoring and Minimum Data Requirement
Nose	Runny or dripping nose Congested or stuffy nose Sneezing Sinus pressure	Arithmetic mean of 4 items Daily score for 3 of 4 items must be present to calculate domain score
Throat	Scratchy or itchy throat Sore or painful throat Difficulty swallowing	Arithmetic mean of 3 items Daily score for 2 of 3 items must be present to calculate domain score
Eyes	Teary or watery eyes Sore or painful eyes Eyes sensitive to light	Arithmetic mean of 3 items Daily score for 2 of 3 items must be present to calculate domain score

Chest/Respiratory	Trouble breathing Chest congestion Chest tightness Dry or hacking cough Wet or loose cough Coughing Coughed up mucus or phlegm	Arithmetic mean of 7 items Daily score for 5 of 7 items must be present to calculate domain score
Gastrointestinal	Felt nauseous Stomach ache Vomit (frequency) Diarrhea (frequency)	Arithmetic mean of 4 items Daily score for 3 of 4 items must be present to calculate domain score
Body/Systemic	Headache Head congestion Felt dizzy Lack of appetite Sleeping more than usual Body aches or pains Weak or tired Chills or shivering Felt cold Felt hot Sweating	Arithmetic mean of 11 items Daily score for 8 of 11 items must be present to calculate domain score
Total	All above 32 items	Arithmetic mean of all 32 items within FLU-PRO In the presence of missing data, the above conditions for the calculation of all domain scores must be met in order to calculate the FLU-PRO total score.

Note: The FLU-PRO questionnaire handled according to the protocol is FLU-PRO version 1.0. The calculation of the Total score is done according to the FLU-PRO user manual version 1.1. Hence following questions from the FLU-PRO v1.0 questionnaire will not be used in the analysis: Swollen throat, Difficulty staying asleep, Difficulty falling asleep, Felt lightheaded, Felt uncomfortable (general discomfort).

- **FLU-PRO total score AUC**

The FLU-PRO total score AUC will be calculated using the FLU-PRO total scores, from baseline to Day 8 and will be estimated for each treatment arm using a mixed model for repeated measurements using a constrained longitudinal data analysis model, similarly as for the composite symptom score AUC in section 4.2.3.

- **Time to return to usual activity and time to return to usual health**

